2 LIST OF ABBREVIATIONS AND DEFINITIONS OF TERMS

Abbreviation	Term
AE	adverse event
β-CTX	beta-C-terminal telopeptide
BID	twice daily
BOR	best overall response
CR	complete response
CBR	clinical benefit rate
CRC	colorectal cancer
CRF	case report form
CSR	clinical study report
CTCAE	Common Terminology Criteria for Adverse Events
DCR	disease control rate
DLT	dose-limiting toxicity
DOR	duration of response
ECOG PS	Eastern Cooperative Oncology Group (ECOG) Performance Status
HCC	hepatocellular carcinoma
IV	intravenous(ly)
LVEF	Left ventricular ejection fraction
MedDRA	Medical Dictionary for Regulatory Activities
ORR	objective response rate
OS	overall survival
P1NP	procollagen type 1 N-terminal propeptide
PD	pharmacodynamic
PFS	progression-free survival
PK	pharmacokinetic
PR	partial response
PT	preferred term
RECIST	Response Evaluation Criteria in Solid Tumours

Abbreviation	Term
RP2D	recommended Phase 2 dose
SAE	serious adverse event
SAP	statistical analysis plan
SD	stable disease
TEAE	treatment-emergent adverse event
WHO	World Health Organization

3 INTRODUCTION

The purpose of this statistical analysis plan (SAP) is to describe the procedures and the statistical methods that will be used to analyze and report results for the Eisai protocol for Study E7386-G000-201 (Amendment 04.1). **CCI**

3.1 Study Objectives

3.1.1 Primary Objectives

Phase 1b part:

- To assess the safety and tolerability of E7386 in combination with pembrolizumab in subjects with previously treated selected solid tumors
- To determine the recommended Phase 2 dose (RP2D) of E7386 in combination with pembrolizumab

Phase 2 part:

- To assess the objective response rate (ORR) of E7386 in combination with pembrolizumab (melanoma, colorectal cancer [CRC], hepatocellular carcinoma [HCC]) according to Response Evaluation Criteria in Solid Tumours ([RECIST](#)) 1.1.

3.1.2 Secondary Objectives

Phase 1b part only:

- To assess tumor response according to RECIST 1.1

Phase 1b and Phase 2 parts:

- To assess duration of response (DOR) according to RECIST 1.1 per tumor cohort
- To assess the disease control rate (DCR: the proportion of subjects with complete response [CR], partial response [PR], or stable disease [SD] after ≥ 5 weeks from the first dose) according to RECIST 1.1 per tumor cohort
- To assess the clinical benefit rate (CBR: the proportion of subjects with CR, PR, or durable SD [duration of SD ≥ 23 weeks]) according to RECIST 1.1 per tumor cohort
- To assess the safety and tolerability of E7386 in combination with pembrolizumab
- To evaluate the pharmacokinetic (PK) profile of E7386 when co-administered with pembrolizumab

3.1.3 Exploratory Objectives

Phase 1b and Phase 2 parts:

3.2 Overall Study Design and Plan

This is an open-label, multicenter, Phase 1b/2 study that will evaluate the safety and efficacy of E7386 in combination with pembrolizumab. **CCI**

CCI Safety, tumor response, PK, and PD assessments will be performed on every subject; details are described in the Schedule of Procedures/Assessments in the study protocol Section 9.5.2.

The study is divided into 3 parts (Phase 1b part, Phase 2 part, and Extension part), and each part will be conducted in 3 phases: Pretreatment Phase (including Screening Period and Baseline Period), Treatment Phase, and Follow-Up Phase (after the End of Treatment [EOT]).

[figure not shown]
Eligible subjects will be enrolled into 1 of 3 tumor cohorts: melanoma, CRC, and HCC.

Study design details are included in the study protocol Section 9.1.

4 DETERMINATION OF SAMPLE SIZE

Phase 1 b part, Dose Escalation

CCI

Phase 2 part, Dose Expansion (E7386 Plus Pembrolizumab Cohorts)

CCI

5 STATISTICAL METHODS

Statistical analyses will be performed by the sponsor or designee after the data cutoff and the database is locked and released. An earlier database lock may also be performed for the purpose of writing a clinical study report (CSR). Statistical analyses will be performed using SAS software or other validated statistical software, as required.

Data cutoff for the primary analyses in the Phase 2 part for each tumor cohort will be performed based on the Efficacy Analysis Set when all subjects have a tumor assessment

until **CCI** and/or have adequate follow-up to be evaluated for DOR, or they have discontinued early due to any cause. The full final analysis will be performed after all subjects complete from the study.

All descriptive statistics for continuous variables will be reported using mean, standard deviation, median, first quantile (Q1), third quantile (Q3), minimum and maximum. Categorical variables will be summarized as number (percentage) of subjects.

5.1 Study Endpoints

For the tumor response related endpoints, the tumor assessments by blinded independent central review (BICR) (if conducted) may be used in the primary analysis for the cohorts in Phase 2 part. Otherwise, tumor assessments by the investigator will be used for the analysis.

5.1.1 Primary Endpoints

- Phase 1b part: Safety related endpoints including DLTs
- Phase 2 part: ORR is defined as the proportion of subjects who have best overall response (BOR) of CR or PR per RECIST 1.1

5.1.2 Secondary Endpoints

- BOR per RECIST 1.1 (for Phase 1b part)
- DOR is defined as the time from the first documentation of CR or PR to the first documentation of disease progression (PD) or death due to any cause (whichever occurs first), in subjects with confirmed CR or PR per RECIST 1.1
- DCR is defined as the proportion of subjects who have a BOR of confirmed CR or PR, or SD (after ≥ 5 weeks from the first dose) per RECIST 1.1
- CBR is defined as the proportion of subjects who have a BOR of confirmed CR or PR, or durable SD (duration of SD ≥ 23 weeks) per RECIST 1.1
- Safety and tolerability (eg, treatment-emergent adverse events [TEAEs], treatment-related adverse events) for E7386 in combination with pembrolizumab
- PK profile of E7386 when co-administered with pembrolizumab

5.1.3 Exploratory Endpoints

5.2 Study Subjects

5.2.1 Definitions of Analysis Sets

5.2.2 Subject Disposition

The number (percentage) of subjects who were screened for the study (ie, those who signed informed consent), continued in the study after screening, failed screening, and the primary reason for screen failures will be presented.

The number (percentage) of subjects who were treated, continued, or discontinued study drug at data cutoff date, along with the primary reason for discontinuation from the study drug will be presented. The number (percentage) of subjects who discontinued treatment but were on survival follow-up at data cutoff date will also be provided.

The number (percentage) of subjects who were on study or off study (ie, discontinued from the study) at data cutoff date and the primary reason for discontinuation from study will be presented.

5.2.3 Protocol Deviations

Important protocol deviation criteria will be established and subjects with important protocol deviations will be identified and documented before the database lock.

The number (percentage) of subjects with at least 1 important protocol deviation and the number (percentage) of subjects with each important protocol deviation, and all protocol deviations related to coronavirus disease 2019 (COVID-19) will be presented.

5.2.4 Demographic and Other Baseline Characteristics

[figure not shown]
Demographic and other baseline characteristics will be summarized using the Efficacy Analysis Set for each dose level/tumor cohort, and for phase/overall (as needed) using descriptive statistics.

Continuous demographic and baseline variables include:

- Age
- Height
- Baseline weight (kg)
- Baseline body mass index (BMI) (kg/m²)

Categorical demographic and baseline variables include:

- Age group:
 - <65 years
 - ≥65
- Sex
- Race
- Ethnicity
- Region/Country
- Eastern Cooperative Oncology Group - Performance Status (ECOG PS)
- New York Heart Association (NYHA) Classification

In addition, previous anticancer medication, previous anticancer procedures and previous radiotherapy will be summarized.

The number (percentage) of subjects in the safety analysis set reporting a history of any medical condition, as recorded on the case report form (CRF), will be summarized.

5.2.5 Prior and Concomitant Therapy

All investigator terms for medications recorded in the CRF will be coded to an 11-digit code using the World Health Organization Drug Dictionary (WHO DD). The number (percentage) of subjects who took prior and concomitant medications will be summarized on the Efficacy Analysis Set for each dose level/tumor cohort, and for phase/overall (as needed) by Anatomical Therapeutic Chemical class 1, pharmacologic class 3, and WHO DD preferred term (PT). Prior medications are defined as medications that started before the first dose of study drug regardless if they were either stopped before the first dose of study drug or continued during the study. Concomitant medications are defined as medications that (1) started before the first dose of study drug and were continuing at the time of the first dose of study drug, or (2) started on or after the date of the first dose of study drug up to 30 days after the subject's last dose. Medications received after 30 days of last dose will be considered as post-treatment medications. The summary will be presented for each dose level/tumor cohort, and for phase/overall (as needed). A medication that cannot be determined as prior/concomitant/post treatment due to missing/incomplete dates will be regarded as a concomitant medication. All medications will be presented in subject data listings.

Any anticancer therapies (medication, procedure) received during survival follow-up and any palliative radiotherapy will also be summarized on the Efficacy Analysis Set.

5.2.6 Treatment Compliance

Records of treatment compliance for each subject will be kept during the study. Clinical research associates will review treatment compliance during site visits and at the completion of the study. Treatment compliance will not be summarized since the data will not be entered in the clinical database. Information on subject exposure to study drug is described in [Section 5.6.1](#).

5.3 Data Analysis General Considerations

5.3.1 Pooling of Centers

Subjects from all centers will be pooled for all analyses.

5.3.2 Adjustments for Covariates

No adjustment for covariates will be performed.

5.3.3 Multiple Comparisons/Multiplicity

No statistical comparison is planned in this study.

5.3.4 Examination of Subgroups

CCI

5.3.5 Handling of Missing Data, Dropouts, and Outliers

No imputation will be performed for missing data.

5.4 Efficacy Analyses

All efficacy analyses (except for DOR) will be performed by dose level in the escalation part and within each cohort/tumor type for the expansion part on the Efficacy Analysis Set. The analysis for DOR will be performed in the subjects who show a confirmed CR or PR within each cohort/tumor type on the Efficacy Analysis Set.

BOR is CR, PR, SD, PD, or not evaluable (NE)/Unknown, where SD has to be achieved at ≥ 5 weeks after the first dose. If a subject had a BOR of non-CR/non-PD, the subject's BOR will be grouped with the SD category. The BOR of CR and PR requires confirmation by a subsequent assessment of response at least 28 days later.

5.4.1 Primary Efficacy Analyses

Phase 1b part:

There is no primary efficacy analysis, since the primary objective of Phase 1b part is to assess the safety and tolerability and determine the RP2D of E7386 in combination with pembrolizumab. Thus, the efficacy analyses for Phase 1b part are described in the subsequent sections according to the study endpoints.

Phase 2 part:

ORR is defined as the proportion of subjects achieving a BOR of CR or PR. All responses of CR and PR must be confirmed no less than 28 days following the initial achievement of the response. Estimated ORR and the corresponding Clopper-Pearson 2-sided 95% CI will be provided for each cohort/tumor type. A summary of BOR will also be presented.

5.4.2 Secondary Efficacy Analyses

BOR per RECIST 1.1 for Phase 1b part will be summarized in the same manner as described above.

Waterfall plots for maximum tumor shrinkage (ie, postbaseline nadir) in sum of diameters of target lesions will be provided.

DOR will be calculated for subjects whose BOR is confirmed CR or PR. It will be estimated and plotted over time using Kaplan-Meier method if necessary. Median and quartiles of DOR will be provided, alongside the 95% CIs. Range (minimum to maximum) of DOR will also be presented with the censored indicator '+' if applicable. The probability of DOR with its 95% CI at selected duration timepoints will be provided. The 95% CIs for the probability of DOR will be calculated. Censoring rules for DOR are the same as those of PFS ([Table 2](#)). Subjects who show a confirmed CR or PR and without disease progression or death will be censored at the time of the last tumor assessment. The summary of subjects with event/censor along with the reason for censor will also be provided.

DCR and CBR will also be calculated. Estimate of DCR and the corresponding Clopper-Pearson 2-sided 95% CI will be presented. CBR will be calculated for subjects whose BOR

is SD. Estimate of CBR and the corresponding Clopper-Pearson 2-sided 95% CI will be presented.

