6 INTERIM ANALYSES

No formal interim analyses requiring database lock are planned. The interim futility data review using a snapshot of the database will be performed by the sponsor for each tumor cohort for consideration of potential cohort expansion in the Phase 2 doublet treatment cohorts. An interim futility data review will be conducted when the initial 15 subjects are enrolled in each tumor cohort and required tumor responses assessed by RECIST 1.1 by the investigator are met or sufficient follow-up are reached. Details of the interim futility data review is described in details in Section 9.7.3 of the study protocol.

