8.2 Efficacy Data Handling

Handling of missing data for tumor assessment result

For the calculation of ORR, DCR and CBR, subjects with missing response status (subjects who do not have adequate postbaseline tumor assessments result) will not be included in numerator, but included in denominator.

Data of tumor assessment result after documented PD or discontinuation from treatment

For the analysis of tumor assessment relevant efficacy endpoints, tumor assessment results after PD or last observation visit (for non-PD subjects) are excluded from the analyses, but included in subject data listing.

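### SAP Section 5.4.2 limits the clinical benefit rate to subjects with best overall response of SD, contrary to the SAP's own definition of that endpoint

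*SAP*

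**What the plan says.** The SAP addresses CBR in five places.

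- **Section 3.1.2 (Secondary Objectives)**, for both the Phase 1b and Phase 2 parts: CBR is "the proportion of subjects with CR, PR, or durable SD [duration of SD" of at least 23 weeks].
- **Section 5.1.2 (Secondary Endpoints)**: "CBR is defined as the proportion of subjects who have a BOR of confirmed CR or PR, or durable SD", again with the 23-week threshold.
- **Section 5.4**, opening paragraph: "All efficacy analyses (except for DOR) will be performed by dose level in the escalation part and within each cohort/tumor type for the expansion part". The population named there is the Efficacy Analysis Set, and only DOR is excepted.
- **Section 8.2 (Efficacy Data Handling)**: for ORR, DCR and CBR alike, subjects with missing response status "will not be included in numerator, but included in denominator".
- **Section 5.4.2 (Secondary Efficacy Analyses)**: "CBR will be calculated for subjects whose BOR". A page break falls at this point, and the sentence then ends by naming SD as the category. The next sentence promises an estimate with a Clopper-Pearson 95% interval.

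The two halves of the Section 5.4.2 sentence join directly. No redaction or gap lies between them.

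**The concern.** The first four places describe a proportion of all subjects in the Efficacy Analysis Set in which responders count as successes. The fifth, which is the sentence that gives the method of analysis, restricts the calculation to subjects whose best overall response is SD. Both cannot be followed.

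The restriction is hard to read as loose phrasing. The same section uses the same construction for DOR, limiting it to confirmed responders, and there it is a real restriction that Section 5.4 confirms. DCR, mentioned just before CBR, carries no restriction. A programmer could reasonably conclude that CBR is meant to be handled as DOR is.

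At stake is a named secondary endpoint of both parts. A figure labelled CBR could be reported that leaves out every responder and has an interval based on the SD subgroup only. A programmer who followed Section 5.1.2 instead would depart from the written method.

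**Working it through.** The SAP gives no numerical CBR, so there is no figure to reproduce. The check is a comparison of the texts followed by an illustration.

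**Step 1: who is in the calculation.** Section 5.4 lists the best overall response categories as CR, PR, SD, PD and not evaluable/unknown, and each subject has one. A subject with SD is therefore not a responder, and a subject without an adequate postbaseline assessment cannot have SD.

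| | Definition (3.1.2, 5.1.2, 5.4, 8.2) | Section 5.4.2 as written |
|---|---|---|
| Numerator | CR + PR + durable SD | durable SD only |
| Denominator | all subjects in the set | SD subjects only |
| Missing response | in denominator | excluded |

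**Step 2: formulas.** Let N be the cohort size, r the confirmed responders, s the subjects with SD, and d those whose SD is durable.

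- Defined CBR = (r + d)/N
- Section 5.4.2 as written = d/s

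Since (r + d)/N = r/N + (s/N)(d/s), the Section 5.4.2 figure is too high when (d/s)(1 − s/N) exceeds r/N, and too low when it falls below r/N. The direction of error is not fixed.

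**Step 3: illustration.** N = 15 is taken from Section 6, where the futility review occurs when the "initial 15 subjects are enrolled in each tumor cohort". The values of r, s and d are assumptions. Intervals are exact Clopper-Pearson 95%, the method named in Section 5.4.2.

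| r | s | d | Defined CBR | Section 5.4.2 as written |
|---|---|---|---|---|
| 0 | 6 | 3 | 3/15 = 20.0% (4.3% to 48.1%) | 3/6 = 50.0% (11.8% to 88.2%) |
| 2 | 6 | 3 | 5/15 = 33.3% (11.8% to 61.6%) | 3/6 = 50.0% (11.8% to 88.2%) |
| 3 | 4 | 4 | 7/15 = 46.7% (21.3% to 73.4%) | 4/4 = 100% (39.8% to 100%) |
| 4 | 6 | 2 | 6/15 = 40.0% (16.3% to 67.7%) | 2/6 = 33.3% (4.3% to 77.7%) |

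Direction check for row 2: (3/6)(1 − 6/15) = 0.30 exceeds 2/15 = 0.13, so the figure is too high. For row 4: (2/6)(1 − 6/15) = 0.20 is below 4/15 = 0.27, so it is too low.

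**Step 4: a larger assumed cohort.** With N = 30, r = 4, s = 12 and d = 5, the defined CBR is 9/30 = 30.0% and Section 5.4.2 gives 5/12 = 41.7%. With r = 2, s = 10 and d = 3, the figures are 5/30 = 16.7% and 3/10 = 30.0%.

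**Step 5: another possible reading.** If the restriction were applied to the numerator only, the result would be d/N. For row 2 that is 3/15 = 20.0% (4.3% to 48.1%), which also differs from the defined 33.3% because the responders are still missing.

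**The case against.** The strongest reply is that this is a drafting slip. The authors probably meant that the duration of SD is derived only for subjects whose best overall response is SD, so as to identify durable SD. Everything else in the SAP supports the full-set calculation: the definition includes responders, Section 5.4 names DOR as the only exception, and the missing-response rule in Section 8.2 would be empty in an SD-only set. Programming specifications and table shells are held in separate documents (Sections 9 and 11) and may already be right.

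The consequence is also bounded. CBR is descriptive, Section 5.3.3 plans no statistical comparison, the primary ORR in Section 5.4.1 does not depend on CBR, and best overall response will be tabulated in both parts, so responders would remain visible.

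Most of this stands as a limit on the consequence. The slip is a plausible explanation, and it cannot be said that the SD-only figure will be produced, only that it will be if the sentence is followed. But the SAP nowhere states the benign intent, and documents not shown cannot be taken to resolve the conflict. The contradiction remains.

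**Conclusion.** The concern holds. Section 5.4.2 contradicts Sections 3.1.2, 5.1.2, 5.4 and 8.2 on a named secondary endpoint, and followed literally it yields the proportion of SD subjects with durable SD in place of the CBR. The conflict lies wholly within the SAP and does not turn on the protocol.

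The size of the error depends on the response counts, which are assumed here. In the cohorts of 15 shown, it ranged from 6.7 percentage points too low (33.3% against 40.0%) to 53.3 points too high (100% against 46.7%). Because the direction varies, a reader could not correct for it from the reported CBR alone. The sentence must be corrected before CBR is analysed, although the primary endpoint is untouched.

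**What to change.** Replace the sentence in Section 5.4.2 with wording such as: *CBR is the number of subjects with a BOR of confirmed CR or PR, plus the number with a BOR of SD lasting at least 23 weeks, divided by all subjects in the Efficacy Analysis Set, by dose level in the Phase 1b part and by tumor cohort in the Phase 2 part, with a Clopper-Pearson 2-sided 95% CI.*

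If the intent was that SD duration is derived only for subjects whose BOR is SD, attach that statement to the SD duration and not to CBR. The programming specification and table shell should be checked against the corrected sentence.

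The cost is one sentence of SAP wording, with no new data and no change to any other analysis.

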5.4.3 Other Efficacy Analyses

OS is defined as the time from the date of first dose to the date of death. All events of death will be included, regardless of whether the event happened while the subject was still taking study drug, or after the subject discontinued study drug. OS will be estimated and plotted over time using the Kaplan-Meier method. Median and quartiles will be provided, alongside 95% CIs. Range (minimum to maximum) of OS will also be presented with the censored indicator '+' if applicable. The probability of OS with its 95% CI at selected timepoints will be provided. Subjects who are lost to follow-up or withdrew consent will be censored at the last known alive date, or the data cutoff date, whichever occurs first. Subjects who remained alive will be censored at the data cutoff date. The summary of subjects with event/censor along with the reason for censor will also be provided.

PFS is defined as time from the date of first dose to the date of the first documentation of disease progression or death, whichever occurs first. PFS will be summarized in the same manner as OS. Subjects without PD or death will be censored at the time of the last tumor assessment. Three-month, 6-month, 9-month, and 12-month PFS rate will be estimated using the Kaplan-Meier method and corresponding 95% CIs will be provided.

Censoring rules for PFS are given in Table 2 below.

Table 2 Censoring Rules for PFS			
No.	Situation	Date of Progression or Censoring	Outcome
1	No baseline or no postbaseline adequate tumor assessments ^a	Date of first dose	Censored
2	Death without disease progression or any new anticancer therapy	Date of death	Progressed
3	Progression documented between scheduled visits, on or prior to new anticancer therapy	Date of the first radiological PD assessment	Progressed
4	Death between adequate assessments (Death before next scheduled assessment or after exactly one missing assessment)	Date of death	Progressed
5	New anticancer treatment started	Date of last adequate radiological tumor assessment ^a prior to or on the date of new anticancer treatment	Censored
6	Death or progression after more than one consecutive missed tumor assessment ^b	Date of last adequate radiological tumor assessment ^a before missed tumor assessment	Censored
7	No progression	Date of last adequate radiological tumor assessment ^a prior to or on the date of data cut-off	Censored

CR = complete response, PD = progressive disease, PFS = progression-free survival, PR = partial response, SD = stable disease.

a. Adequate tumor assessment is radiological assessment of CR, PR, SD, non-CR/non-PD, or PD as determined by investigators at regular interval as defined in the protocol. Any tumor assessments after new anticancer treatment starts will be removed in the definition of PFS.

b. More than 1 consecutive missed tumor assessment is defined as if the duration between the last adequate radiological tumor assessment and PD or death is longer than 97 days [$=((6+1) \times 2 \times 7) - 1$] for subjects on the every 6 weeks scanning schedule in this study; longer than ($>$) 139 days [$=((9+1) \times 2 \times 7) - 1$] for subjects on every 9 weeks tumor assessment schedule after **CCI** in this study

For subjects moving from one schedule to another:

Missed **CCI** and Week 33 assessments: ($>$)118 days [$=((6+1) + (9+1)) \times 7 - 1$]

The priority of the censoring rules is as follows:

If the subject had PD (No. 3) or death (No. 2, No. 4) prior to or on the date of data cut-off, the following sequence will be applied:

- If the No. 1 is applicable, the date of first dose will be used (censored). However, if the subject died (No. 2, No. 4) within 97 days (14 weeks -1 day) after the first dose and did not meet No. 5, the date of death will be the PFS event date (not censored).
- If the No. 5 before PD or death, and/or No. 6 are applicable, the earliest date of censoring will be used (censored).
- Otherwise, the earliest date of progression (No. 2, No. 3, No. 4) will be the PFS event date (not censored).

If the subject had neither PD (No. 3) nor death (No. 2, No. 4) prior to or on the date of data cut-off, the earliest date of censoring (No. 1, No. 5, No. 6, No. 7) will be used (censored), if the subject met multiple situations.

Censoring rules for OS are provided in Table 3 below.

Table 3 Censoring Rules for OS

No.	Situation	Date of Death or Censoring	Outcome
1	Death before or on data cut-off	Date of death	Death
2	Death after data cut-off	Date of data cut-off	Censored
3	Alive at data cut-off	Date of data cut-off	Censored
4	Lost to follow-up or withdrawal of consent before data cut-off	Date last known to be alive	Censored

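### Does the overall survival censoring table need a rule for what shows that a subject is alive at the cut-off?

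*SAP*

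**What the plan says.** SAP section 5.4.3 gives the endpoint as "OS is defined as the time from the date of first dose to the date of death". It then sets two censoring rules in the text:

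- Lost or withdrawn, taking the earlier of two dates: "Subjects who are lost to follow-up or withdrew consent will be censored at the last known alive date, or the data cutoff date, whichever occurs" (…).
- Everyone else not known to have died: "Subjects who remained alive will be censored at the data cutoff date".

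Table 3 in the same section has four rows: death by the cut-off (event), death after the cut-off (censored at the cut-off), "Alive at data cut-off" (censored at the cut-off), and "Lost to follow-up or withdrawal of consent before data cut-off" (censored at the date last known alive). The section also requires a breakdown of censoring: "The summary of subjects with event/censor along with the reason for censor will also be provided".

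Two other places bear on the point. Section 5.2.2 expects a group of subjects who "discontinued treatment but were on survival follow-up at data cutoff date". Section 5 ties the Phase 2 primary cut-off to tumour assessment (the time is redacted) "and/or have adequate follow-up to be evaluated for DOR, or they have discontinued early due to any cause".

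**The concern.** Neither the text nor row 3 says how a subject is shown to be alive at the cut-off, for example by a contact on or after that date. Consider a subject who has stopped treatment, is in survival follow-up, was last contacted some weeks before the cut-off, and has not been declared dead, lost or withdrawn. No row names this subject, and two dates are open: the cut-off, or the date last known alive. The visible part of the Phase 2 cut-off trigger carries no condition on survival status.

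The choice of date can matter. Censoring at the cut-off credits survival time that nobody observed. If some of these subjects have died without the site yet knowing, the Kaplan-Meier curve is too high. Left to programming, the date would be chosen after the data are in hand.

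**Working it through.** **1. Text against table.** The two agree for each status:

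| Status | Section 5.4.3 text | Table 3 |
|---|---|---|
| Dead by cut-off | event | row 1, event |
| Dead after cut-off | not separately named | row 2, cut-off |
| Alive | cut-off | row 3, cut-off |
| Lost or withdrawn | last known alive or cut-off, the earlier | row 4, last known alive |

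A subject who is not dead, lost or withdrawn falls into row 3 by elimination. Section 5.2.2 treats being in survival follow-up as a status held at the cut-off, which fits row 3. Row 2 can operate only if some survival information from after the cut-off reaches the database. That does not prove a complete status update, but it makes it unlikely that no survivor is ever re-contacted.

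**2. Size.** The SAP gives no figure to reproduce. It states no median OS, contact interval, accrual period or OS landmark, so every input here is an assumption: exponential survival with median 9 months, contact every 3 months, gap from last contact to cut-off uniform on 0 to 3 months, 400,000 simulated subjects per scenario. True 12-month OS is 0.5^(12/9) = 0.397. Let p be the share of deaths in the gap that are known, and q the share of survivors confirmed at the cut-off. Each cell gives 12-month OS with cut-off censoring / with last-known-alive censoring.

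| Accrual / cut-off (months) | p=0, q=0 | p=1, q=0 | p=q=0.8 |
|---|---|---|---|
| 12/15 | 0.477 / 0.399 | 0.397 / 0.322 | 0.413 / 0.398 |
| 12/18 | 0.435 / 0.396 | 0.396 / 0.358 | 0.404 / 0.396 |
| 18/21 | 0.435 / 0.397 | 0.397 / 0.363 | 0.404 / 0.397 |
| 18/24 | 0.422 / 0.398 | 0.398 / 0.377 | 0.403 / 0.398 |
| 12/24 | 0.400 / 0.396 | 0.396 / 0.392 | 0.396 / 0.396 |

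- At p=q=1 the two dates coincide for every subject, so the difference is 0.
- At p=q=0.8 the largest difference is 0.413 − 0.398 = 1.5 points.
- The largest difference overall, 0.477 − 0.399 = 7.8 points, needs no survivor re-contacted and a cut-off 3 months after the last enrolment. Follow-up then runs from 3 to 15 months, so only (15 − 12)/12 = 25% of subjects could reach 12 months, about 4 of 15. At 6 months the same scenario differs by 2.8 to 2.9 points.

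**3. Which date is better.** In the p=0 column, last-known-alive censoring is close to the truth and cut-off censoring is too high. In the p=1 column the order reverses: cut-off censoring is right, and last-known-alive censoring is too low, by 0.397 − 0.322 = 7.5 points in the 12/15 case. If survivors are confirmed more often than gap deaths are found (p=0.25, q=0.5, 12/15), both are too high, at 0.456 and 0.417. Neither date is uniformly better.

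**4. Against the noise.** The half-width 1.96·√(0.397 × 0.603 / n) is 0.248 at n = 15 and 0.175 at n = 30. Fifteen is the size at the futility review in section 6; 30 is an assumed cohort.

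**The case for a change.** The strongest case for a change is that the censoring table is where such a definition belongs, that each censoring must be given a reason, and that one line would settle the date in advance. A separate simulation with other assumptions (medians of 8, 12 and 18 months, contact every 6, 12 or 24 weeks, 6 to 18 months to cut-off) found cut-off censoring too high by 1.3 points (64.3% against 63.0%) to 8.2 points (43.6% against 35.4%), with last-known-alive censoring nearly unbiased. Section 8.1 adds to the case: in imputing partial death dates it calls the last known alive date the survival censoring date, which does not match row 3.

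Part of this stands. The evidence for being alive is not spelled out, and a sentence would be helpful. The rest is weaker:

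- The near-unbiased result holds because that simulation lets deaths become known only through scheduled contacts. When deaths are reported between contacts but survivors are not re-contacted, last-known-alive censoring is the biased choice.
- The section 8.1 wording is loose, but it applies only to subjects who died and does not set the date for the living.
- The missing pieces, namely the contact schedule, a status check at the cut-off and when an uncontacted subject counts as lost, are commonly set in the protocol, which was not available for this review. SAP section 3.2 itself refers to the protocol for the assessment schedule.

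**Conclusion.** No change to the plan is needed. This is a gap in detail that analysts fill sensibly, and the rule itself is not shown to be wrong. Row 3 takes the subjects in question by ordinary reading. With survival status confirmed for all, the choice of date makes no difference; with 80% confirmed it is worth at most 1.5 points of 12-month OS. The larger figures depend on assumed inputs outside the SAP, chiefly that no survivor is re-contacted and that the cut-off follows soon after the last enrolment. Replacing the cut-off with the last contact would exchange a possible upward bias for a possible downward one, so without a status update there is no clear gain.

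The consequence is also limited. OS is neither a primary nor a secondary endpoint in section 5.1, section 5.3.3 plans no comparison, and the objective response rate does not use these rules. The conclusion would weaken if the protocol provided no survival follow-up around the cut-off and many subjects were last contacted long before it.
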